#### **7.1.2 Treatment period**

The study treatment duration is 48 weeks. Patient visits will occur weekly for the first 3 weeks of treatment and then every 4 weeks starting from Week 5 until Visit 777 (EOT).

Having completed the screening period, patients who are eligible will be enrolled and randomized to receive either deferasirox DT or deferasirox granules. The target daily dose is calculated by the physician based on the patient's actual body weight.

At the start of treatment, iron chelation naïve patients will receive either deferasirox DT 20 mg/kg once daily or deferasirox granules 14 mg/kg once daily. All ICT pre-treated patients will use a deferasirox DT or an equivalent strength-adjusted granules starting dose corresponding to their pre-washout dose, please refer to [Appendix 14.1](#).

For details on study design and dose adjustments, see [Section 4](#) and [Section 6.2](#).

For details of assessments during the treatment periods, see [Table 7-1](#) and [Table 7-2](#).

After the core phase has ended, the patients who have participated and completed the 48 weeks core treatment phase as per protocol and do not have access to the new formulation will have the possibility to enter the optional extension treatment phase until there is local access to the new formulation (granules or FCT) or up to 5 years, whichever occurs first. If the patient does not enter the optional extension phase they must complete the core EOT visit, 30 day safety follow up and EOS visit.

- Patients who discontinue prior to Visit 17 will complete Visit 777 within 7 days of last dose of study drug. End of study (Visit 778) and safety follow-up will be performed within 30 days last dose was given in the core phase.
- All patients who have completed the core treatment phase per protocol will have an EOT visit (Visit 777) at Week 49. Patients who opt to continue to the optional extension treatment phase will proceed to [Table 7-2](#) to complete the Visit 17 assessments on the same day. At completion of the optional extension treatment phase, or should patients discontinue at any time after starting the extension treatment phase they will complete the End of Treatment of Optional Extension Phase (Visit 779) within 7 days of last dose of study drug. End of study (Visit 780) and safety follow-up will be performed within 30 days last dose was given in the optional extension phase.

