**Table 2-1      Definition of core and extension phases**

Core phase			Extension phase		
Treatment	Start date	Stop date	Treatment	Start date	Stop date
Granules	Date of first IC signed	Minimum[Date of latest administration of Granules in core phase + 30 days, cut-off date, Visit 17 date – 1 day]	Granules	Visit 17 date	Date of the last administration of Granules in extension + 30 days
DT	Date of first IC signed	Minimum[Date of latest administration of DT + 30 days, cut-off date, Visit 17 date – 1 day]	Granules	Date of first administration of Granules	Date of the last administration of Granules in extension + 30 days

Only data with an assessment date or event start date (e.g. vital sign assessment date or start date of an adverse event) in the core phase will be summarized in the interim and primary analysis.

Summaries will be based on:

- Core phase comparing data for Granules versus DT formulations (blue rectangle in [Figure 2-1](#)).
- Entire granule period of patients randomized to Granule combining core and extension phases (dark green rectangle in [Figure 2-1](#)) side-by-side with Granules for patients randomized to DT who switched to Granules in extension phase (light green rectangle in [Figure 2-1](#)). Cross-over treatment group corresponds to the patients randomized to DT who switched to Granules in the extension phase.

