**Table 2-1** **Definition of core and extension phases**

Core phase			Extension phase		
Treatment	Start date	Stop date	Treatment	Start date	Stop date
Granules	Date of first IC signed	Date of last treatment of granules + 30 days	No treatment	Nil	Nil
DT	Date of first IC signed	Date of last treatment of DT + 30 days	No treatment	Nil	Nil
Granules	Date of first IC signed	date of first administration of granules in extension phase* – 1 day	Granules	date of first administration of granules in extension phase*	Date of the last administration of Granules in extension + 30 days
DT	Date of first IC signed	Date of first administration of granules* – 1 day	Granules	Date of first administration of Granules*	Date of the last administration of Granules in extension + 30 days

[figure not shown]
\*including 0 doses for patients to identify the extension start date only

Summaries will be based on:

- **Core phase\*** - comparing data for Granules versus DT formulations (blue rectangle in [Figure 2-1](#)).
- **Extension phase\*:** summaries will only display extension phase data from patients randomized to Granules (light blue rectangle in [Figure 2-1](#)) side-by-side with patients randomized to DT who switched to Granules in extension phase (light green rectangle in [Figure 2-1](#)). Cross-over treatment group corresponds to the patients randomized to DT who switched to Granules in the extension phase.
- **Entire granule period** - patients randomized to Granules combining core and extension phases (dark green rectangle in [Figure 2-1](#)) side-by-side with Granules for patients randomized to DT who switched to Granules in extension phase (light green rectangle in [Figure 2-1](#)). Cross-over treatment group corresponds to the patients randomized to DT who switched to Granules in the extension phase.

\*Note for exception to [Table 2-1](#): For analyses by time point in patients who continue into extension phase, EOT-core assessments done at the beginning of extension phase will be displayed in core phase reports.

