#### On-treatment period

For the core phase, the overall observation period will be divided into three mutually exclusive segments taking into account stop rules as per [Table 2-1](#):

- Pre-treatment period: from day of patient's first informed consent to the day before first dose of study drug;
- On-treatment period: from day of first dose of study drug to 30 days after last dose of study drug *for patients who do not enter the extension phase*; from day of first dose of study drug in the core phase to one day prior to the start of the first dose of study drug in the extension phase *for patients who enter the extension phase*.

- Post-treatment period: starting at day 30+1 after last dose of study treatment.

For the entire granule period, the following conventions will be taken into account while deriving the three observation periods above:

- For patients enrolled in DT formulation in the core phase, the pre-treatment period will not be derived;
- For patients enrolled in Granule formulation in the core phase, the first dose of study drug will be the day of first dose in the core phase.

Unless otherwise specified, the safety summary tables will include only assessments from the on-treatment period.

All data, regardless of observation period, will be listed. Safety assessments starting during the pre-treatment or post-treatment period will be flagged in the listings. Safety assessments starting prior to study day 1 will appear with negative study day in the listings.

Any COVID-19 related safety events will be flagged in listings.

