#### **4.1.2     Laboratory data and vital signs**

Laboratory data (biochemistry, hematology and urinary parameters as well as serum creatinine, creatinine clearance and proteinuria) and vital signs will be collected at screening visits, at each regularly patient visit and at end of treatment visit.

If two or more assessments are performed within a time window then the assessment closest to the planned visit is used in analyses by time window. When two values are equidistant from the planned assessment, the later one is used in analyses. When multiple values are reported on the same day then the average value is used in analyses. For parameters with categorical results, the one from central laboratory is used in analyses.

For worst post-baseline assessment, all on-treatment values are considered regardless of time windows.

[Table 4-2](#) shows the defined time windows.

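### The core phase closes the day before Visit 17, yet the end-of-core visit falls on the Visit 17 day for patients who continue; the later repair leaves the worst-value core tables uncovered

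*SAP*

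**What the plan says.** **Protocol, 7.1.2.** "All patients who have completed the core treatment phase per protocol will have an EOT visit (Visit 777) at Week 49". Patients who continue then move to the extension schedule "to complete the Visit 17 assessments on the same day". Section 7.1 repeats the same-day rule and gives its reason, which is to avoid a treatment gap.

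**SAP Amendment 3, 2.1 and Table 2-1.** The core phase stops in the granules arm at "Minimum[Date of latest administration of Granules in core phase + 30 days, cut-off date, Visit 17 date – 1 day" and in the DT arm at "Minimum[Date of latest administration of DT + 30 days, cut-off date, Visit 17 date – 1 day". Below the table, only data dated "in the core phase will be summarized in the interim and primary analysis". Section 3, which lists departures from the protocol, has no entry. Yet the footnote to Table 4-2 maps the end-of-core visit to the week-49 window, and section 2.8.5 plans 48-week summaries for FAS-1, FAS-2 and FAS-3.

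**End of Core SAP.** Table 2-1 moves the core stop date to the day before the first extension administration, counting zero-dose records. A note makes an exception for analyses by time point: "EOT-core assessments done at the beginning of extension phase will be displayed in core phase reports". In section 2.9.6, the core on-treatment period of patients who continue still runs only "to one day prior to the start of the first dose of study drug in the extension phase". Section 4.1.2 adds: "For worst post-baseline assessment, all on-treatment values are considered regardless of time windows". Section 4.1.4 says the same for eye data.

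**Final SAP.** Table 2-1 keeps that stop rule without the note, and section 2.1.6 ties the observation periods to it. Section 2.7.6.4 presents the worst LOCS III change for Safety Sets 1 to 3 as well as Safety Set 4.

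**The concern.** Visit 777 is the only scheduled core visit after a full 48 weeks of randomised treatment. In Amendment 3, a date rule that always closes the phase one day earlier conflicts with that SAP's own week-49 outputs. It acts selectively, because only patients who continue are affected, and continuing depends on benefit or wish and on local access.

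The worst-value tables matter separately because they ignore visit windows and depend wholly on which values count as on-treatment. A deterioration first recorded at week 49 after 48 weeks of DT should appear in the DT core column. If it does not, and the same value is then the reference for changes on granules (End of Core SAP, 2.7), neither column registers it. Eye data are the most exposed. Protocol Table 7-3 schedules only two post-baseline core photograph sessions, Visit 11 and Visit 777, so a patient can lose one of two.

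**Working it through.** **1. The plan's week-49 mapping (Table 4-2).** Week = 5 + 4k; planned day = (week − 1) × 7 + 1; window = planned day − 14 to + 13. With k = 11:
- week = 5 + 44 = 49
- planned day = 48 × 7 + 1 = 337
- window = days 323 to 350

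This reproduces the footnote that places the end-of-core visit in week 49.

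**2. Visit 777 against the Amendment 3 stop date.** The protocol allows ± 7 days, so Visit 777 falls on days 330 to 344. Let D be the shared day of Visits 777 and 17. The core phase then ends no later than D − 1.

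| D | Latest core stop | In week-49 window? | In core phase? |
|---|---|---|---|
| 330 | 329 | yes | no |
| 337 | 336 | yes | no |
| 344 | 343 | yes | no |

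**3. Can another scheduled visit fill the window?** Week 45 (k = 10) is planned on day 44 × 7 + 1 = 309, so it falls on days 302 to 316. All are before day 323. Only unscheduled values could fill the window.

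**4. Compliance.** The endpoint is a cumulative ratio of counts consumed to counts prescribed. Counts are taken at weeks 5, 9, …, 45 and at Visit 777, giving 48 / 4 = 12 four-week intervals. Losing Visit 777 removes at most 1 of 12 (8.3% of treatment time), and the patient stays in the analysis.

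**5. Co-primary time point.** Week 25 (k = 5) is day 24 × 7 + 1 = 169, window days 155 to 182. Visit 17 cannot affect it.

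**6. Worst-value tables in the End of Core SAP.** Let E be the date of the first extension-dose record. Core on-treatment ends at E − 1.
- If E = D, Visit 777 is outside the core on-treatment period.
- If E = D + 1, it is inside.

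Inclusion therefore depends on how the first extension record is dated, not on whether the assessment came before that dose. This governs the laboratory shift tables and the worst logMAR change. For DT switchers, the pre-granule reference is the last value on or before the start of granules, so Visit 777 is that reference in either case.

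**7. Final SAP.** Table 5-6 places the week-49 visit of patients who continue in the end-of-core window, but section 5.3.4 disregards windows for worst values. The rule in step 6 then applies to LOCS III, if the Safety Set 1 to 3 tables are core-phase tables as in End of Core SAP 2.9.6. The final SAP does not say so outright.

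**8. Size.** The Amendment 6 rationale reports 67 patients ongoing in the extension in June 2021, so at least 67 entered: 67 / 216 = 31.0% of the maximum enrolment. The split by prior chelation is not given.

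**The case against.** The strongest reply is that the completed-core 48-week results belong to the End of Core report, and that its SAP handles these patients. Besides the note to Table 2-1, the Table 4-2 footnote maps their end-of-core visit to week 49, Table 4-4 does so for eye data, and section 2.9.1 has its own end-of-core compliance rule. This stands for analyses by time point. A reader might infer that week-49 data are lost from the core analyses generally; the End of Core SAP shows they are not.

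Amendment 3 can also be called self-contradictory rather than clearly exclusionary, since its ocular table defines the end-of-core value by visit. That is fair, but it states no exception to its date rule, so a programmer must choose.

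For worst values, End of Core SAP 4.6.1 includes all post-baseline values. That wording is broader than section 4.1.2 and could be read as admitting Visit 777. But section 2.9.6 limits safety summaries to on-treatment assessments by default, so the sections leave the matter unresolved at best. It is also true that a first extension dose taken the next day puts Visit 777 inside the core period.

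Other tempting inferences go too far:
- **That 48-week compliance mainly describes patients who did not continue.** The ratio is cumulative; only the last interval is at risk.
- **That the date rule alone meets the 10% trigger for multiple imputation.** Section 2.8.5 states that trigger for FAS-1. The naive share of the 67 is unknown, as is the number past Visit 17 at the May 2018 cut-off, when some patients had not reached week 49 anyway.
- **That week-49 changes are attributed to no formulation at all.** This can arise only for DT switchers in worst-value tables. By-visit core tables still show the value, and patients randomised to granules keep their original baseline over the entire granule period.

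**Conclusion.** The point holds in two parts. First, Amendment 3 contradicts itself: as written, its core stop date excludes the scheduled week-49 assessments that its own window and 48-week summaries require. Second, the repair in the End of Core SAP is limited to analyses by time point. Its worst post-baseline core tables, and the final SAP's worst LOCS III change for Safety Sets 1 to 3, still exclude a Visit 777 value dated on the first extension-dose day. For DT switchers, a change first seen then may be missing from both worst-value columns.

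The number of patients affected is not given; at least 67 entered the extension. The conclusion assumes that Visits 777 and 17 took place on one day, as scheduled. The second part also assumes a first extension-dose record dated that day and, for LOCS III, that the Safety Set 1 to 3 tables are core-phase tables. The co-primary endpoints are untouched, and the 48-week summaries are descriptive. A reader might conclude that the primary study report's 48-week tables are wrong; the documents do not show which rule was programmed, so that has to be checked.

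**What to change.** In Table 2-1 and in the on-treatment definition of each SAP, state that assessments recorded under Visit 777 and taken before the first extension dose belong to the core phase and the core on-treatment period for all analyses, including worst post-baseline tables. Add that the same values may also serve as the pre-granule reference for DT switchers.

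State in the End of Core SAP that a same-day Visit 777 count qualifies for 48-week compliance. Say in the final SAP which phase the Safety Set 1 to 3 LOCS III tables cover.

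Then check whether any 48-week tables in the primary report were produced under the literal Amendment 3 rule.

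The cost is a sentence or two per SAP, a change to the phase flag, and a rerun of the worst-value tables. No new data are needed.

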**Figure 2-1      Core and extension phases**

## General analysis conventions

**Pooling of centers:** Unless specified otherwise, data from all study centers will be pooled for the analysis. Due to expected small number of patients enrolled at centers, no center effect will be assessed.

**Qualitative/categorical data** (e.g., sex, race) will be summarized by frequency counts and percentages. Percentages will be calculated using the number of patients in the relevant treatment arm or subgroup as the denominator.

**Continuous data** (e.g., age, body weight) will be summarized using appropriate descriptive statistics (i.e. mean, standard deviation, median, minimum, and maximum) by treatment arm. Lower and upper quartiles will also be presented when applicable.

## 2.2 Analysis sets

### All screened patients

A patient is considered to be screened into the study if they have signed the study informed consent/assent form. Only patients who have signed informed consent will be included in the All screened patients analysis set.

### Screen failures

Screen failures analysis set includes all patients who have been screened and who failed to be randomized for any reason (i.e. failing to meet inclusion or exclusion criteria or any other screening procedure).

### Safety Set

The Safety Set 1 will consist of all ICT naïve patients (as per eCRF) who received at least one dose of the study drug during the core phase.

The Safety Set 2 will consist of all ICT pre-treated patients (as per eCRF) who received at least one dose of study drug during the core phase.

The Safety Set 3 will consist of all patients who received at least one dose of study drug during the core phase.

The Safety Set 4 will consist of all patients who received at least one dose of granule formulation during the core or extension phase.

Patients will be analyzed according to the treatment actually received and strata information recorded in the eCRF.

Treatment actually received is defined as the treatment the patient received at the first day of study medication in the core phase.

### Full Analysis Set

Full Analysis Set (FAS) is defined according to the Intention to Treat (ITT) principle.

The Full Analysis Set 1 (FAS-1) consists of all ICT naïve (as per IRT, see [Section 4.5](#)) randomized patients.

The Full Analysis Set 2 (FAS-2) consists of all ICT pre-treated (as per IRT) randomized patients.

The Full Analysis Set 3 (FAS-3) consists of all randomized patients.

Following the intent-to-treat principle patients are analyzed according to the treatment and stratification factors they were assigned to at randomization during the core phase.

### **Per-protocol set**

The Per-Protocol Set (PPS) will consist of all ICT naïve patients from the FAS-1 without any major protocol deviation.

The major protocol deviations that will lead to exclusion of patients from the PPS are listed below:

- No transfusion dependent anemia (ID=I05);
- Serum ferritin  $\leq 1000 \mu\text{g/L}$  at Screening (ID=I07);
- First administered study medication different from medication assigned by randomization (ID=S02);
- Absence of serum ferritin assessment at baseline and at least 1 post-baseline assessment (ID=G28);
- Any safety-related exclusion criteria met (ID= E01A3, E02A3, E03A3, E05, E06, E07, E08, E09, E10, E11, E13, E14, E18A4 or E19);
- No dose-adjustment for efficacy due to change in serum ferritin at weeks 13 and 25 (ID=S11 at weeks 13 or 25);
- Intake of any prohibited concomitant medication (ID= M01, M03, M04 or M05).
- Strata assigned for randomization differs from strata reported by investigator on CRF (ID=G32).

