	The dose of deferasirox DT or granules should be adjusted if necessary every 3 months based on the trends in serum ferritin and investigator's judgement. ICT naïve patients can adapt dose after 4 weeks. Dose adjustments need to be made in steps of 5 or 10 mg/kg/day for deferasirox DT and of 3.5 or 7 mg/kg/day for deferasirox granules and are to be tailored to the individual patient's response and the therapeutic goal of (reduction of iron burden). In patients not adequately controlled with deferasirox DT doses of 30 mg/kg/day, doses of up to 40 mg/kg/day may be considered. In patients not adequately controlled with deferasirox granules doses of 21 mg/kg/day, doses of up to 28 mg/kg/day may be considered. The starting dose and the dose adjustment considerations must take into account that the therapeutic goal is reduction of iron burden (as opposed to maintenance of iron burden). Doses above 40 mg/kg/day for deferasirox DT and above 28 mg for deferasirox granules are not allowed.

Dose modifications for deferasirox	
500 – 1000 ng/mL	Dose reductions in steps of 5 to 10 mg/kg/day for deferasirox DT and of 3.5 or 7 mg/kg/day for deferasirox granules is required to maintain serum ferritin levels within the target range.
< 500 ng/ml	Interruption of study treatment is required until serum ferritin rises above 500 ng/mL
Changes in urine protein/creatinine ratio	
For patients who develop proteinuria or a worsening of pre-existing proteinuria (assessed by a dipstick) at any visit, urine samples should be collected and assessed by the central laboratory. [Egypt: Local laboratory] In case of a single increase of the urinary protein/creatinine ratio the assessment should be repeated at the next visit.	
> 0.5 (mg/mg) in two consecutive second-void urine samples (a minimum of 48h apart), if all other causes of proteinuria have been excluded.	Deferasirox dose reduction by 50%  When resolution of UPCR (<0.5mg/mg) at the next study visit, dose can be resumed again at 100%  If increase in UPCR >0.5mg/mg recurs again within 2 months after initial increase, therapy needs to be reduced to 50% of the last dose. If increase in UPCR does not recur after 2 months at reduced dose (50%) , study medication can be returned to 100% of the last dose

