### **2.8.1 Variable**

All analyses for the primary objective will be performed on the FAS-1 and presented by treatment group: deferasirox DT and deferasirox granule formulation.

The co-primary efficacy variables are:

- Compliance measured by stick pack /tablet count based on amount of medication dispensed, returned and reported as lost/wasted by the patient or caregiver in the eCRF, over 24 weeks of treatment (i.e. assessed at week 25 visit). Compliance will be calculated as the ratio of total count consumed to total count prescribed, where
  - total count consumed is derived from cumulative dispensed, returned and lost/wasted counts over 24 weeks of treatment (i.e. assessed at week 25 visit);
  - total count prescribed is derived from cumulative prescribed count over 24 weeks of treatment (i.e. assessed at week 25 visit).

The prescribed count corresponds to the count prescribed by the investigator for the relevant visit period that the patient should have taken during this period. For each strength (125 mg, 250 mg and 500 mg tablets for deferasirox DT; 90 mg, 180 mg and 360 mg tablets for deferasirox granule), the prescribed count for the relevant visit period is calculated from the daily prescribed count at the beginning of this period multiply by the duration (days) of this period. The duration of a period will be calculated as (end date of

the period) – (start date of the period) + 1. The total count prescribed is the sum of counts prescribed per strength.

- Change from baseline in serum ferritin after 24 weeks of treatment (i.e. assessed at week 25 visit).

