## 2.8.4 Supportive analyses

The following supportive analyses will be provided:

- The primary analysis as described in [Section 2.8.2 & Section 2.8.3](#) will be also performed for the PPS, FAS-2 and FAS-3 as supportive efficacy analyses;
- In addition, descriptive summaries will be provided for the FAS-1 by treatment arm:
  - Summary of absolute and relative change from baseline values in serum ferritin assessed at week 25 visit and 95% confidence intervals for means (see [Table 4-2](#) for time window definition);
  - Summary statistics of overall compliance measured by stick pack/tablet count assessed at week 25 visit and 95% confidence intervals for means. Patient who discontinued before the week 25 visit will be included in the compliance endpoint calculation.

These descriptive analyses will be repeated by the age stratification factor, by average actual daily dose category, by baseline serum ferritin category, and underlying disease (see [Table 2-6](#)).

- A forest plot of mean difference between treatments will be presented with absolute change in serum ferritin after 24 weeks of treatment and the corresponding exact 95%CI including these subgroups. Point estimates and 95% CI will be generated.
- If more than 10% of patients have no serum ferritin value after 24 weeks of treatment, sensitivity analysis will be performed for the primary analysis for serum ferritin using multiple imputation method. This analysis will be performed for the FAS-1.

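### The per-protocol set excludes patients for a dose decision at week 25, the endpoint visit itself, so membership partly depends on the outcome

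*SAP*

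**What the plan says.** The PPS definition is in section 2.2 of the SAP for the primary analysis (Amendment 3). The set "will consist of all ICT naïve patients from the FAS-1 without any major protocol deviation", and one listed deviation is "No dose-adjustment for efficacy due to change in serum ferritin at weeks 13 and 25 (ID=S11 at weeks 13 or 25".

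Section 2.8.1 of the same SAP defines the endpoints. The ferritin endpoint is "Change from baseline in serum ferritin after 24 weeks of treatment (i.e. assessed at week 25 visit"). The compliance endpoint closes at the same visit: the "total count prescribed is derived from cumulative prescribed count over 24 weeks of treatment (i.e. assessed at week 25 visit").

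Protocol Table 6-2 says what drives an efficacy adjustment. "The dose of deferasirox DT or granules should be adjusted if necessary every 3 months based on the trends in serum ferritin" and on the investigator's judgement. At ferritin of 500 to 1000 ng/mL, a dose reduction "is required to maintain serum ferritin levels within the target range"; below 500 ng/mL, interruption is required.

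SAP section 2.8.4 gives the PPS its role: the primary analysis "will be also performed for the PPS, FAS-2 and FAS-3 as supportive efficacy analyses".

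**The concern.** A per-protocol exclusion should pick out departures that could have distorted the endpoint. A dose change made or omitted at the week-25 visit comes after the ferritin measurement period and after the 24-week count period, so it can distort neither. Whether a change was called for at that visit, however, is read from the ferritin course up to that visit. The week-25 part of the criterion therefore selects patients on the quantity being compared.

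The trial is open-label and adjustment rests partly on judgement, so the deviation could occur at different rates in the two arms. If it does, the PPS comparison is biased even with no true difference.

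The bullet also contains two rules: its text joins weeks 13 and 25 with *and*, its deviation code with *or*.

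A likely origin, though this is inference, is Protocol Amendment 5, which moved the primary time point from 48 to 24 weeks. Under a 48-week endpoint, week 25 was a mid-course visit.

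**Working it through.** **1. Does the wording matter?** Classify patients by whether the deviation (S11) was recorded at each visit.

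| S11 recorded at | *and* reading | *or* reading | Week 13 only (proposed) |
|---|---|---|---|
| Neither visit | kept | kept | kept |
| Week 13 only | kept | excluded | excluded |
| Week 25 only | kept | excluded | kept |
| Both visits | excluded | excluded | excluded |

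The two readings give different sets. On both, week-25 status decides membership for some patients: those without S11 at week 13 under *or*, those with it under *and*. This holds whether S11 means that no adjustment was made or that an indicated adjustment was not made.

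**2. The plan's own figure.** SAP section 2.11 uses 45 per arm, a difference of 450 ng/mL, SD 900 and one-sided 5%. The noncentrality is 450 / (900 × √(2/45)) = 2.37. Power is 76.1% by the noncentral t and 76.6% by the normal approximation, against 76% stated. The 450 and 900 are carried into the illustration.

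**3. Illustration.** Assumed, not in the documents: change is normal with SD 900; the DT mean is 0; a share p of patients whose ferritin rose (change above 0) is excluded. For an arm with mean m:

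- share at risk: Q = Φ(m/900)
- their contribution to the mean: E = m·Φ(m/900) + 900·φ(m/900)
- mean of those kept: (m − pE) / (1 − pQ)

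No true effect (m = 0 in both arms): Q = 0.5 and E = 359.05.

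- p = 0.25: −89.76 / 0.875 = −102.6
- p = 0.50: −179.52 / 0.75 = −239.4
- Equal p: difference 0.
- Granules 25%, DT 50%: −102.6 − (−239.4) = **+136.8**, against granules.
- Granules 50%, DT 25%: **−136.8**, favouring granules.

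In absolute size this is 136.8/450 = 30% of the design effect.

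True difference −450 (granules m = −450): Q = 0.3085 and E = −138.8 + 316.9 = 178.0.

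- p = 0.50 in both arms: granules (−450 − 89.0) / (1 − 0.1543) = −637.3. The difference is −637.3 + 239.4 = **−398**. Exclusions are 15.4% on granules and 25.0% on DT.
- p = 0.25 in both arms: the difference is −433.

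**4. Which tail is removed sets the sign.** If exclusions fell instead on patients whose ferritin fell, symmetry under no true effect turns the kept means into +102.6 and +239.4. Granules/DT rates of 25%/50% would then give −136.8 rather than +136.8.

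**5. Effect on a one-sided 5% t-test.** Simulation with 48 per arm, no true effect, patients with rising ferritin excluded, 20,000 runs per scenario:

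| Shares excluded, granules/DT | Bias (ng/mL) | One-sided error |
|---|---|---|
| none | about 0 | 4.8% |
| equal (20% or 50%) | about 0 | 5.0–5.3% |
| 30%/20% | −48 | 8.1% |
| 40%/20% | −101 | 12.6% |
| 50%/25% | −138 | 16.8% |
| 20%/40% | +97 | 1.7% |

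**The case against.** A reader might infer that the rule strips out non-responders and so flatters granules. The documents do not support that. Entry requires ferritin above 1000 ng/mL, so the bands in which Table 6-2 requires a reduction or interruption are reached by patients whose ferritin fell. For other patients the table asks for adjustment only if necessary, where an omission is harder to call a deviation. S11 could remove good responders, poor responders or both. Even if it removed only patients with rising ferritin, the sign would depend on which arm has the higher rate.

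The full definition of S11 is in a separate deviation document (VAP Module 3, cited in SAP section 2.4) that is not available here. It may mean an indicated adjustment that was not made, and with central-laboratory testing the week-25 result may not have been back at the visit. These points limit what can be said about mechanism and size. They do not make a week-25 decision precede the week-25 endpoint.

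The PPS is one of several supportive analyses. Section 2.4 tabulates PPS-excluding deviations by arm, and section 2.2 lists excluded patients. That helps a reader see an imbalance, but it does not remove the selection, and section 2.4 does not promise a split by visit.

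The *and*/*or* pair can be read as naming the two visits checked, with the code as the operating rule. That is plausible, but a programmer should not have to guess.

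**Conclusion.** The point holds for the week-25 part of the criterion. It excludes patients for a decision that cannot have affected either co-primary endpoint and that depends on the ferritin course leading to one of them. The week-13 part precedes the endpoint and does not share this defect.

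Direction and size are not known from the documents. Under the stated assumptions the bias with no true effect is zero for equal rates and about 137 ng/mL either way for rates of 25% and 50%. A true −450 shrinks to about −398 when half of those with rising ferritin are excluded in both arms. The zero cut-off, the DT mean and every rate are assumptions.

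A reader might also infer that the primary result is compromised. It is not: success is judged on FAS-1, which this criterion does not touch. The End of Core SAP states that the study did not meet its primary objective; nothing here alters that. What is weakened is the PPS as a check on the ferritin comparison.

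**What to change.** For the 24-week PPS, count S11 only when it precedes the week-25 ferritin sample, that is, at week 13, and replace the *and*/*or* pair with that single rule. Make the same change in the deviation list. This alters an analysis set only; no dosing rule changes.

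The primary analysis is already reported, and section 2.8.4 of the End of Core SAP says its supportive analyses will not be repeated. A wording change alone would therefore not reach the existing result. Wherever the PPS result is used, report the number excluded for S11 at week 25 by arm, and show the PPS analysis without those exclusions, labelled post hoc. The cost is one line of SAP and deviation-list text, one count by arm, and one re-run of an existing ANCOVA on a redefined set.
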